### **3.2 Allocation to Intervention Groups and Blinding**

Participants will be randomly assigned to the intervention or enhanced usual care condition at the baseline assessment. Please see section 8.1.1 for further information. It will not be possible to conceal intervention condition from the PI, study coordinator, and members of the intervention team, but research assistants involved in data collection will be blind to study condition.

### **3.3 Study Duration, Enrollment and Number of Sites**

#### **3.3.1 Duration of Study Participation**

The study duration per subject will be up to 6 months (24 weeks), to accommodate families needing to reschedule any assessments or intervention sessions. After screening and, for eligible families, enrollment, a baseline assessment will occur within 0-3 weeks. One to 3 weeks following the baseline assessment, the enrolled family randomized to the intervention condition will participate in Sleep Well! over 6-8 weeks. The post-intervention will occur 1-2 weeks after the end of the intervention phase for those randomized to Sleep Well!, or at weeks 9-16 for those in the control condition. The follow-up assessment condition will occur 6-8 weeks after the post-intervention assessment. Thus, the duration of study participation is between 15 and 24 weeks.

#### **3.3.2 Total Number of Study Sites/Total Number of Subjects Projected**

CHOP and the University of Oregon are the two sites involved in this study. All participant procedures, including recruitment and data collection, will occur at the 3 CHOP-affiliated urban primary care sites in Pennsylvania (South Philadelphia, Cobbs Creek, and Karabots). No study recruitment, data collection, or other participant procedures will occur at University of Oregon. Only data management, analysis, and interpretation will occur at University of Oregon.

### **3.4 Study Population**

#### **3.4.1 Inclusion Criteria**

- 1) Parental/guardian permission (informed consent)
- 2) Caregiver participant is the parent or legal guardian of the child subject
- 3) Caregiver/legal guardian  $\geq 18$  years of age.
- 4) Child between the ages of 1 and 5 years.
- 5) Presence of caregiver-reported child sleep problem determined by a Brief Child Sleep Questionnaire item included in an eligibility screening questionnaire (see below) or child meets American Academy of Sleep Medicine diagnostic criteria for either pediatric insomnia or insufficient sleep, assessed through an eligibility screening questionnaire.
- 6) English-speaking.

### 3.4.2 Exclusion Criteria

- 1) Caregiver is not parent or legal guardian of child participant.
- 2) Presence of a child neurodevelopmental (e.g., autism spectrum disorder; Trisomy 21) or chronic medical condition or concern (e.g., sickle cell disease, cancer) in which the disorder or treatment of the disorder impact sleep.
- 3) Caregivers/guardians or subjects who, in the opinion of the Investigator, may be non-compliant with study schedules or procedures.

Subjects that do not meet all of the enrollment criteria may not be enrolled. Any violations of these criteria must be reported in accordance with IRB Policies and Procedures.

## 4 STUDY PROCEDURES

### 4.1 Screening Phase

Procedures for screening referred and potentially eligible participants are described in detail above (section 3.1.1). The screening phase will be completed by a study team member and will include:

- EMR review by a study team member
- Phone screening using eligibility screening questionnaire (section 5.1.2), after completing verbal HIPAA authorization
- Scheduling of informed consent and baseline assessment (completed in person or electronically)

### 4.2 Baseline Assessment (Pre-Intervention)

The baseline assessment will be conducted by a study team member and will be completed in person or electronically. It will include:

- Informed consent
- Abstraction of child demographic information and previous behavioral health or sleep services (EMR)
- Caregiver completion of caregiver demographic and family information questionnaire, previous treatment questionnaire, Brief Child Sleep Questionnaire, and Child Behavior Checklist
- Caregiver completion of the Center for Epidemiological Studies Depression Scale, Revised (CES-D-R), PROMIS Sleep Disturbance Short Form, and coronavirus (COVID-19) and Other Life Stressors questionnaire
- Randomization to study condition (see 3.1 and 8.1 for further information)
- 7-day daily sleep diary questionnaire via text messages delivered via REDCap and its integration with Twilio
- 7-day actigraphy

If a caregiver has difficulty completing measures independently, a research assistant will read the items and provide assistance as needed. If a caregiver is unable or unwilling to

receive the 7-day diary via text messages, we will offer to (a) e-mail the daily diary to the caregiver for 7 days or (b) have a research assistant call the caregiver by phone to administer the daily diary verbally for 7 days, with the research assistant entering caregiver responses into a REDCap database.

### **4.3 Study Treatment Phase**

#### **4.3.1 Intervention condition**

Sleep Well! will be provided over approximately 6-8 weeks, to allow for families to reschedule sessions as needed, and will include 3 sessions. Intervention sessions will typically last about an hour, but session length may vary. Content is delivered in a modular format based on family goals and the child's sleep concern (e.g., using electronics before bedtime; an inconsistent bedtime routine; etc.). To ensure high-quality care, intervention providers will receive regular supervision. Providers will also contact families by phone between sessions (3 times total) to (a) promote attendance, engagement, and implementation of Sleep Well! strategies, (b) assist in resolving barriers to treatment, and (c) guide families to community resources as needed. As noted above (3.1.2), text messages about the intervention will also be sent to families via Twilio and its integration with REDCap. For ethical reasons, families will be informed that they have the right not to participate in the study. If they choose not to participate, they will be referred to their pediatrician, who may provide the family with additional referrals to the CHOP Sleep Center or other behavioral health services, consistent with the current standard of care at CHOP.

Intervention sessions that occur in-person, via HIPAA-compliant video, or by telephone will be audio-recorded to monitor fidelity. Telephone check-in calls will not be audio-recorded. After each intervention session and intervention-related phone call, the interventionist will document which intervention contents were used using an intervention-specific fidelity checklist. The study interventionist will also document any feedback regarding the intervention as a method to assess intervention feasibility and usability. In addition, approximately 2 weeks into the intervention phase caregivers will complete a brief survey about their child's sleep electronically via REDCap (mid-point assessment).

#### **4.3.2 Procedures for training Sleep Well! interventionists**

[name], a licensed psychologist who is also a Diplomat in Behavioral Sleep Medicine, will train and supervise all study interventionists, who are doctoral-level or post-doctoral level clinical psychology trainees at CHOP. [name] will provide each interventionist with approximately 8 hours of training prior to intervention. Interventionists will be trained to implement the treatment manual and attend to process variables, including establishing trust, listening actively, and re-directing tangential comments. All interventionists are mandated child abuse reporters and will be trained to identify and report child abuse and any other concerns related to participant safety. Consultation and peer supervision related to intervention delivery will occur weekly with [name] mentor, [name], Associate Director of the CHOP Sleep Center and Diplomat in Behavioral Sleep Medicine.

---

### 4.3.3 Control (enhanced usual care) condition

The enhanced usual care condition will occur for between 6 and 8 weeks. At randomization to this condition, participants will be provided with an evidence-based sleep guidelines for young children. These guidelines are summarized in the CHOP Parent Family Education manual and have been reviewed and approved by pediatric sleep experts (including study Co-I [name] and co-I [name]) and CHOP primary care physicians. Participants in this condition will also be able to consult with their primary care physician for management of child sleep. Consistent with usual care in the CHOP system, the primary care physician may manage the sleep concern or choose to make a referral to the CHOP sleep center or to other behavioral health services internal or external to the CHOP system. Of note, the CHOP Parent Family Education handouts provide contact information for the CHOP Sleep Center and direct readers to follow-up with their primary care provider for further guidance.

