### Study Design:

This is a randomized controlled trial (RCT). Caregiver-child dyads will be assigned to the intervention group, in which they participate in the Sleep Well! behavioral sleep intervention, or to an enhanced usual care control group, in which they are provided with an evidence-based sleep education handout.

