## **3 INVESTIGATIONAL PLAN**

### **3.1 General Schema of Study Design**

This is a randomized control trial of Sleep Well!, a behavioral sleep program for toddlers and preschoolers. As shown in Figure 1, following referral, potentially eligible families will be screened by phone for intervention eligibility. Eligible and interested participants will be scheduled for a pre-intervention (baseline assessment) visit that occurs in-person or by electronically and includes informed consent (or e-consent), random assignment to the intervention condition or an enhanced usual care condition, and completion of baseline measures. The baseline assessment will occur 0-3 weeks post-screening. Those assigned to the intervention group will start receiving the intervention 1-3 weeks following baseline assessment. Those in the control condition will be given a Parent-Family Education Manual handout about healthy sleep in early childhood and directed to follow-up with their pediatrician. The Sleep Well! intervention phase includes 3 sessions conducted in-person, by HIPAA-compliant video conferencing platform, or by telephone, as well as 3 telephone check-ins over a 6- to 8-week period (study weeks 1-6 to 7-14). A mid-point assessment of child sleep will occur electronically for the intervention condition 2 weeks into the intervention phase. The post-intervention assessment will occur at week 9-16 (1-3 weeks post last intervention session for intervention group). The follow-up assessment will occur 6-8 weeks after the post-intervention assessment, or at week 15-24.

Outcomes related to intervention feasibility and acceptability will be assessed throughout the duration of the study period (see Table 1, above). Caregiver participants will complete baseline demographic information and ratings of their child's sleep. Actigraph devices will be used to objectively measure sleep. At post-intervention, caregiver participants will also provide ratings of their child's sleep, their own sleep, mood, and stress, and those who were in the intervention condition will participate in a qualitative interview to provide intervention content and delivery feedback. Similar measures will be administered at post-intervention. At this time, caregivers in the control condition will also complete an interview to identify perspectives about their enhanced usual care experience.

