## 8 STUDY ADMINISTRATION

### 8.1 Treatment Assignment Methods

#### 8.1.1 Randomization

Participants will be randomly assigned to the intervention or enhanced usual care condition at the baseline assessment. The randomization sequence will be generated by a study statistician. Randomization will be maintained by keeping a separate, password-protected list in REDCap that lists subject ID and group assignment.

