#### 8.1.2 Blinding

Families and Sleep Well! interventionists will not be blinded to condition assignment. In addition, it is not possible for the Co-I [name] or the Study Coordinator to be

blinded to condition assignment. However, all other members of the study team involved in data collection will be blinded to intervention group assignment. Blinding will be maintained by keeping a separate, password-protected list in REDCap that lists subject ID and group assignment. This database will be accessible only to the Co-I ([name]) and the Study Coordinator.

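### Nothing holds disclosure of arm or the control handout until the 7-day baseline actigraphy ends, so time zero for the only objective outcome can be recorded with the arms unequally exposed

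*Combined protocol and SAP*

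**What the plan says.** Section 8.1.1 places allocation within the baseline visit: "Participants will be randomly assigned to the intervention or enhanced usual care condition at the baseline assessment". Section 3.1 describes that visit as consent, then "random assignment to the intervention condition or an enhanced usual care condition, and completion of baseline measures". Section 4.2 gives an unnumbered list in which the questionnaires come first, then "Randomization to study condition (see 3.1 and 8.1 for further information"), then the 7-day diary and the 7-day actigraphy.

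The two arms meet their study material at different times. For controls, section 4.3.3 says: "At randomization to this condition, participants will be provided with an evidence-based sleep guidelines for young children". The abstract defines the control group as one "in which they are provided with an evidence-based sleep education handout", so the handout is the part of the control condition that the study itself supplies. For the other arm, section 3.1 says: "Those assigned to the intervention group will start receiving the intervention 1-3 weeks following baseline assessment".

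Section 8.1.2 states: "Families and Sleep Well! interventionists will not be blinded to condition assignment". The restricted allocation list described there keeps assignment from data collectors, not from families.

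In section 6.4 the growth model sets its intercept at the pre-intervention assessment and reads the effect from the group-by-time interaction. Actigraphic nighttime sleep duration is a listed secondary outcome, and actigraphy is the only measure that Table 1 labels objective.

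**The concern.** A baseline should be measured before either arm is exposed to anything specific to that arm. If the order in section 4.2 is followed, control families can have the sleep guidelines in hand for all 7 recording days. Sleep Well! families normally have had no session by then but know that treatment is coming. The 1-3 week gap delays exposure in one arm only.

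The bias could go either way. An early gain in controls raises their baseline, shrinks their apparent improvement and favours Sleep Well!. Anticipatory change in the Sleep Well! arm does the reverse. Section 1.3 reports that sleep education lengthened sleep in lower-SES children, but those were other programmes in children without sleep problems, and no one-week effect is given. This shows only that a shift is possible.

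The outcome is secondary, but section 6.5 gives estimating effect sizes for a later, fully powered trial as the study's main goal. Section 6.4 draws those effect sizes from this interaction.

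Two smaller gaps belong here. Sections 3.1 and 4.2 list randomisation and the questionnaires in different orders. Section 4.3.3 gives the length of the control phase (6-8 weeks) but not the day it starts.

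**Working it through.** **1. Sequence.** The plan states no figure for this point, so the passages are set side by side.

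| Event | Timing as written | Section |
|---|---|---|
| Randomisation | at the baseline assessment | 3.1, 3.2, 8.1.1 |
| Place in the list | after questionnaires, before 7-day diary and actigraphy | 4.2 |
| Control handout | at randomisation | 4.3.3 |
| Sleep Well! starts | 1-3 weeks after baseline | 3.1, 3.3.1 |
| Families told their arm | unblinded; day not stated | 8.1.2 |
| Rule to wait for the end of recording | none found | – |

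Exposure during the recording can be up to 7 of 7 days in controls and is normally 0 of 7 days of session content in the Sleep Well! arm.

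**2. Weight of the baseline value.** Take three visits at times t₀ = 0, t₁, t₂, balanced and complete, with random intercept and slope. The slope weight on the baseline value is (t₀ − t̄)/Σ(t − t̄)². A baseline shift h in controls only changes the between-arm difference projected to t₂ by h × t₂ × t̄/Σ(t − t̄)².

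For weeks (0, 9, 15), t̄ = 8 and Σ = 64 + 1 + 49 = 114, so the weight is 15 × 8/114 = 1.053. In the same way:

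| Visit weeks | Weight |
|---|---|
| 0, 7, 13 | 1.024 |
| 0, 10, 18 | 1.033 |
| 0, 9, 15 | 1.053 |
| 0, 16, 24 | 1.071 |
| 0, 7, 15 (minimum) | 0.976 |
| 0, 16, 22 (maximum) | 1.077 |

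The minimum and maximum come from a grid with post-intervention 7-16 weeks after baseline and follow-up 6-8 weeks later.

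- The lower end is the control arm if its phase starts at randomisation: 6 + 1 = 7 weeks to 8 + 2 = 10 weeks. If it starts after the same 1-3 week gap, the range is 1 + 6 + 1 = 8 to 3 + 8 + 2 = 13 weeks.
- Section 4.5 counts follow-up from the end of the intervention phase, while section 3.1 counts it from the post-intervention assessment. Allowing a 4-8 week interval leaves the range at 0.976 to 1.077.

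**3. Illustration (assumed shift).** The documents give no handout effect. Assume a 5-minute gain in controls only, and assume that the 30-40 minute medium effect in section 6.5 applies to actigraphy, which the section does not say.

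- Added to the estimate: 5 × 0.976 = 4.9 minutes to 5 × 1.077 = 5.4 minutes.
- Share of the medium effect: 4.9/40 = 12% to 5.4/30 = 18%.

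**4. Would the baseline t-test detect it?** Section 6.5 equates 0.5 SD with 30-40 minutes, so the SD is 30/0.5 = 60 to 40/0.5 = 80 minutes. Five minutes is then 5/80 = 0.063 to 5/60 = 0.083 SD. For a two-sided 5% t-test with 1:1 allocation (level and ratio assumed):

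| Per arm | Chance of a flag |
|---|---|
| 40 | 5.9-6.6% |
| 50 | 6.1-7.0% |

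With no true difference it is 5%. The rule in section 6.4 that turns significantly different baseline outcomes into covariates uses the same recordings, so it cannot tell chance imbalance from early exposure.

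**The case against.** The strongest objection is that the order is inferred. The list in section 4.2 is unnumbered, the 7-day recordings are themselves part of the baseline assessment, and randomising at the end of that assessment would fit the wording. Figure 1, the study diagram, was not visible in the text reviewed and might show the order. This stands, and it is why the finding is that exposed recording can happen, not that it will.

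The scope is also narrow. One listed actigraphy outcome is affected, the diary supplies no listed secondary outcome, and section 4.2 lists the questionnaires before randomisation. A handout that section 3.1.3 calls consistent with usual care may change little in a week. These points limit the likely size but do not supply the missing rule.

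On the arithmetic, study weeks appear to be counted from screening: 0-3 plus 1-3 weeks gives the stated start at weeks 1-6. On that clock, 16 weeks after baseline is not reachable and the maximum weight falls slightly, to about 1.074-1.076. The range also assumes balanced, complete data. With mixed visit times the weight ran from about 0.97 to 1.27, depending on the variance components and the projection time. Allowing for dropout as well, it was still about 1.05 to 1.09 at the mean last visit. So 0.98-1.08 is not a strict bound, but a weight of about one stands.

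Finally, it can be said that logging the dates of randomisation, disclosure and recording would be enough. Logging would reveal early exposure but would not prevent it, and the exposure cannot be undone once the data are collected.

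**Conclusion.** The concern holds. As written, the plan allows the time-zero actigraphy to be recorded after controls have received their study material and before Sleep Well! families have started. A baseline-week arm difference from that cause would enter the estimated effect at about its full size. The size and direction of any such shift cannot be derived from the documents, and the 5-minute case is an illustration only.

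Confidence is medium because the sequence is inferred from list order and from when controls receive the guidelines. The matter should be fixed before enrolment. It bears on secondary effect estimates and on the design of the later trial, and does not touch the primary endpoints.

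**What to change.** In sections 3.1, 4.2, 4.3.3 and 8.1.1, state that:

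- baseline questionnaires are completed before randomisation, which makes sections 3.1 and 4.2 agree;
- disclosure of arm and release of the control handout wait until the 7-day diary and actigraphy window closes, whether or not the recording is complete;
- the control phase starts on a named day, with the study-week windows restated to match.

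Record the dates of randomisation, disclosure, and first and last actigraphy night.

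Section 8.1.2 already limits the allocation list to the co-investigator and the study coordinator, so the coordinator can make the disclosure contact. The section 3.2 commitment that "research assistants involved in data collection will be blind to study condition" is then preserved.

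The cost is protocol wording and one contact per dyad (80 planned, at most 100). The wait uses up to 7 days of the 1-3 week gap before Sleep Well!, leaving 7 − 7 = 0 to 21 − 7 = 14 days, so the study team must reconcile the windows. The sample size does not change.

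Moving randomisation itself to the end of the window is optional. It may lose some dyads before allocation (number not estimable from the documents) and would require rewording the randomisation metric in section 6.4. Holding only disclosure and the handout avoids both.

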## 4.4 Post-intervention assessment

The post-intervention assessment will be completed approximately 1-2 weeks following the end of the intervention phase for Sleep Well! participants or following the end of the control phase for the enhanced usual care condition participants. Post-intervention will be conducted by a study team member and will be completed in person or electronically (questionnaires) and via telephone (interview for Sleep Well! participants). It will include:

- Caregiver completion of the Brief Child Sleep Questionnaire, Child Behavior Checklist, previous treatment questionnaire, Center for Epidemiological Studies Depression Scale, Revised (CES-D-R), PROMIS Sleep Disturbance Short Form, and COVID-19 and life stressors questionnaire
- 7-day daily sleep diary questionnaire via text messages delivered via REDCap and its integration with Twilio
- 7-day actigraphy
- EMR review of any behavioral health or sleep services
- For Sleep Well! intervention participants only:
  - Caregiver completion of the Treatment Evaluation Inventory—Short Form, Multicultural Therapy Competency Inventory- Client Version (MTCI-CV), and Goal Attainment measure
  - Audio-recorded caregiver interview on intervention content and acceptability

If a caregiver has difficulty completing measures independently, we will follow procedures as outlined above in section 4.2.

## 4.5 Follow-Up Phase

The follow-up assessment will be conducted approximately 6-8 weeks after the end of the intervention phase. The assessment will be conducted by a study team member and will be completed in person or electronically (questionnaires) and via telephone (interview for enhanced usual care participants only). It will include:

- Caregiver completion of the Brief Child Sleep Questionnaire, Child Behavior Checklist, Center for Epidemiological Studies Depression Scale, Revised (CES-D-

R), PROMIS Sleep Disturbance Short Form, and COVID-19 and life stressors questionnaire

- EMR review of any behavioral health or sleep services
- 7-day daily sleep diary questionnaire via text messages delivered via REDCap and its integration with Twilio
- 7-day actigraphy
- For enhanced usual care participants only:
  - Caregiver interview about sleep services

If a caregiver has difficulty completing measures independently, we will follow procedures as outlined above in section 4.2.

